Palliative care (PC)	PC is care that improves the quality of life of patients and their loved ones who are facing a life-threatening condition or frailty, by preventing and relieving suffering through early identification, assessment, and treatment of problems of a physical, psychological, social and spiritual nature.
Quality of life	An individual's perception of their position in life in the context of culture and value system in which they live and in relation to their goals, expectations, standards and concerns
WMO	Medical Research Involving Human Subjects Act (Wet Medisch-wetenschappelijk Onderzoek met Mensen)

1. INTRODUCTION AND RATIONALE

The majority of patients with a life-limiting illness experience symptoms, impairing the quality of life(1). In 2017, a total of 150.000 individuals died in the Netherlands, of whom the vast majority had cancer (41%), cardiac disease (24%) or dementia (16%)(2). The most common experienced symptoms during the last phase of life are fatigue, pain, lack of energy, weakness, lack of appetite and dyspnoea(3,4). The intensity of these symptoms increases as death approaches, in particular the last two months of life(5). To improve the quality of life of patients with a life-limiting illness and family caregivers, adequate palliative care (PC) has proven to be essential(6–8). The World Health Organisation (WHO) defines PC as *“an approach that improves the quality of life of patients (adults and children) and their families who are facing problems associated with life-threatening illness. It prevents and relieves suffering through the early identification, correct assessment and treatment of pain and other problems, whether physical, psychosocial, or spiritual”*(9). Multiple studies have shown that PC interventions are associated with a lower symptom burden, greater advance care planning, fewer hospitalizations, lower healthcare expenses, enhanced communication between healthcare professionals and patients, enhanced emotional support, higher patient satisfaction and even improved survival(6,10–14).

PC provided by nursing teams working in primary care, is indispensable for 68% of Dutch population that prefers to stay at home during the last phase of life. However, merely 36% actually dies at home(15,16). The study conducted by Reyniers et al. presents several explanations for inappropriate hospitalization near the end of life. Patients were admitted to the hospital when symptom control (55%) at home was insufficient according to the patient, family was convinced care was better (54%) at the hospital or patients felt safer (35%) at the hospital(17). Nurses play a prominent role in providing PC at home, since they are responsible for the detection of signs and symptoms, the performance of multidimensional assessments, the collaboration of a wide range of disciplines and the communication with patients and their families(18). Additionally, General practitioners (GP) often rely on nurses to optimally assess these needs and report this information back. However, previous studies have shown multiple barriers in the provision of PC by nursing teams working in homecare organizations, which are: the identification of patients with PC needs, the collaboration with GPs and other caregivers, knowledge on quality of PC at home and optimizing autonomy, communication, and competences(19). As a result, patients with a life-limiting illness suffer concurrently from multiple symptoms that are often undetected, impairing the quality of life and making it impossible to stay at home. Family caregivers are also known to be susceptible to emotional, social, physical, and financial distress due to the heavy duty of taking care of a friend or loved one who is no longer able to care for themselves(20). One in ten family caregivers in the Netherlands is overburdened(21). Hence, symptom management in patients and family caregivers dealing with a life-limiting illness, living at home in the Netherlands is suboptimal.

In order to enhance a systematic approach of PC in primary healthcare, the Palliative Reasoning (PR) methodology has been developed(22). This is a stepwise, iterative, multidimensional symptom management approach consisting of a preparatory phase, followed by four phases(23,24).

Multidimensional symptom management plays a central role in this approach and is defined as “the treatment of symptoms while taking the physical, psychological, social and spiritual aspect of the

problem into account"(25,26). Due to the number of components, the flexibility of the intervention to fit different contexts and the effect interaction it has with the context, the implementation is considered to be complex. Therefore, the development and implementation strategy of PR is based on the Medical Research Council (MRC)-model, figure 1, which is a framework that is commonly used for developing and evaluating complex interventions(27).

[figure not shown]

Figure 1. The MRC-model(27).

Prior research revealed the need for a systematic symptom management approach and supportive tools to support clinical decision making and multidisciplinary collaboration, by homecare nursing teams(28). Hence, the feasibility of the PR methodology has recently been tested in primary care. However, the effect of this methodology on symptoms of patients remains unknown. To further develop, optimize and successfully implement the PR methodology in future primary care practice and to improve the quality of life of patients and family caregivers, we aim to determine the effect of the PR methodology on the perceived symptoms of patients and family caregivers dealing with a life-limiting illness, receiving palliative homecare.

2. OBJECTIVES

Primary Objective: The primary objective of this study is to determine the effect of the PR methodology on perceived symptoms of patients and family caregivers dealing with a life-limiting illness and receiving palliative nursing care at home by teaching home care nursing teams the PR methodology and compare it with usual care provided in the Netherlands.

Secondary objectives:

- To adequately and systematically identify patients with a life-limiting illness in need of palliative care by implementing the surprise question in daily practice of nursing teams.
- To adequately and systematically identify, analyse and treat symptoms of patients and caregivers dealing with a life-limiting illness by implementing the PR methodology.

3. STUDY DESIGN

To determine the effect of the PR methodology, a pragmatic open-label multicenter cluster randomized controlled trial (cRCT) will be conducted in nursing teams working in primary care, from January 2024 to March 2026 in Utrecht, the Netherlands. We define a cluster as one nursing team in primary care, which is a group of registered nurses (RNs) and nurse assistants (NAs) collaborating within one home care organization and within the same district with support of specialized nurses (SN) and/or nurse practitioners (NPs). The trial consists of an intervention group and a control group. To enhance heterogeneity of usual care in the control groups and limit the risk of bias, randomization of the intervention will be conducted within one primary healthcare organization.

The intervention starts with the adequate identification of patients in need of palliative care by means of the surprise question “would I be surprised if this patient dies in the next year?”. If the answer to the question is “no”, the patient is suitable for receiving palliative care. After identification the PR methodology is followed by four phases. step 1: map out the individual situation, symptom burden and quality of life of the patient, step 2: summarize the current problems and develop a proactive policy plan, Step 3: evaluate the effect of the proactive policy plan on the symptom burden and quality of life of the patient, step 4: adjust the policy plan if necessary and continue evaluating. The Utrecht Symptom Diary – four dimensional (USD-4D) will be used to monitor the individual situation, symptom burden and quality of life of patients, as described in step 1. This is a Patient Reported Outcome Measure (PROM) and is validated in palliative care populations.

The nursing teams selected as control group will continue to provide usual care to patients with a life-limiting illness. We define usual care as “care that patients with a life-limiting illness, living at home, would be expected to receive as part of normal practice from that specific homecare organization”(29). To gain insight into normal practice of the control group, we will consult the organization’s current safety standards, guidelines, and protocols. Additionally, questions regarding normal practice will be asked during interviews with healthcare professionals.

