5.1.2. Secondary study parameters/endpoints

The Quality of life of patients is assessed at enrolment, at one, three and six months by means of the EORTC QLQ C15 pal(33). This is a 15-item questionnaire developed by the European Organisation for research and treatment of cancer Quality of Life Group. The questions are answered on a scale from 1 to 4, in which the number 1 refers to “not at all”, 2 refers to “a little”, 3 refers to “quite a bit” and 4 refers to “very much”. The EORTC QLQ C15 pal is a shorted version of the original EORTC QLQ C30 pal, which is specifically developed for palliative care. To optimize the feasibility of measures, this shortened version will be used to reduce the risk of missing items and decrease the burden on participating patients.

Symptom burden of patients is assessed at enrolment, at one, three and six months by means of the Utrecht Symptom Diary Four Dimensional (USD4D), which is a patient reported outcome measure (PROM)(34). The USD4D comprises of questions regarding the physical, psychological, social, and spiritual dimension, which are rated on a scale from 0-10 (0 = symptom is absent to 10 = severity symptom is the worst imaginable).

Primary caregiver burden is defined as the perceived burden of the individual that is faced with the primary responsibility of taking care of a disabled friend or loved one. The primary caregiver burden Is assessed at enrolment, one, three and six months by means of the Self Rated Burden Scale, which is a one item numerical scale answering the question “How do I perceive the care for my loved one at the moment?”(35–38). The question is answered on a scale of 0 to 10, in which 0 refers to “not at all straining” and 1 refers to “much to straining”. In

addition, the perceived burden of informal care (Dutch: Ervaren Druk Informele Zorg (EDIZ)) will be used, assessing aspects of informal care contributing to the perceived burden(39).

The EDIZ is developed for the use in caregivers of patients suffering from dementia at home, however, this measurement instrument is widely used to assess the level of burden of caregivers of patients with a life-limiting illness. This instrument contains 9 statements to which patients must answer “no!”, “no”, “more or less”, “yes” or “yes!”.

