5.2. Study procedures

Firstly, this study will start with the assessment of team characteristics, to develop a suited implementation strategy that fits the team and local context but does not influence the fidelity of function. Depending on the composition of the team, education levels and competences in the team, education and training content will be established by a team of coaching experts,

consisting of independent NPs and GPs with extensive experience in PC and PR. The intervention group will be educated in identifying patients with PC needs and will be taught how to apply PR in a four-day training with practical assignments. After two weeks of providing this four-day training to the nursing team, team coaches will be coached by means of a coaching on the job trajectory once a fortnight by the team of expert coaches. Team coaches that will be trained work as NP or SN within one of the organizations and are teamed up with RNs of the general nursing team. The team coaches will perform day to day coaching on the job. The implementation of the intervention will take approximately one month and will be planned in collaboration with the teams and the coaches.

Additionally, nurses who are enrolled in the study will be invited to complete questionnaires individually at enrolment and at six months about their own current symptom management practices, roles and responsibilities, collaboration, communication, and competences.

Secondly, the research team will perform an assessment of baseline measurements in participating patients and request to complete a questionnaire regarding demographic characteristics. The assessment of baseline measurements will be performed by post, mail, telephone, or teleconsulting depending on what is the most suitable and least burdensome for the patient. Subsequently, patients will complete at one-, three- and six-months a questionnaire containing questions regarding symptom control, quality of life and symptom burden. If these questionnaire reveals that a patient does not suffer from any symptoms, it will be excluded from the study. However, the excluded patients will be asked to complete the Lastmeter questionnaire to detect symptoms that may develop at a later stage, to be able to reconsider their inclusion in the study. After each questionnaire and/or assessment patients will be offered support of a NP, specialised in PC to talk about possible thoughts or concerns raised by completing the questionnaires.

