Lastly, an assessment of demographic characteristics and perceived care burden on the primary caregiver is performed by the research team. Thereafter, at one-, three- and six-months perceived care burden is evaluated by telephone using the EDIZ rating scale. After each assessment the primary caregiver will be offered support of a NP, specialised in PC to talk about possible thoughts or concerns raised by completing the questionnaires.

Blinding:

In causal studies, blinding is performed ideally at participant, data collection and data analysis level. In this case, however, blinding at the analysis level is the only feasible.

- The participants are not blinded. Patients, primary caregivers, and the nursing teams will all be aware of their allocation to the intervention group, since the method Palliative Reasoning will be implemented in daily care.
- The data collection will not be performed blindly. Firstly, the data are collected by local nurses who are aware of their allocation. Secondly, the research team who is involved in training the participants are also aware of the allocation, which is necessary to ensure an in-depth exploration of the experiences of the nursing team

during the up-following qualitative part of this study. This part will be described in a different research protocol, which is part of phase 4 of this study.

- Data analysis will be performed blinded. The researcher performing the data analysis will be blinded for the group allocation using labels. The labels will be opened after the analysis.

Randomization and allocation:

The clusters will be randomized through a simple randomization method with the Clinical Trial Randomization Tool from the National Cancer Institute(40,41). To minimize the risk of allocation bias, we will stratify between both homecare organization. The teams are informed about their allocation by the research team.

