1.15 Last check date by datamanager

2023-07-25

1.16 Indicate which laws and regulations are applicable for the project (please check all that apply)

- Richtlijn Kwaliteitsborging Mensgebonden Onderzoek (Quality Assurance for Research Involving Human Subjects)
- Nederlandse gedragscode wetenschappelijke integriteit
- Gedragscode Gezondheidsonderzoek (Dutch)
- Wet op de Geneeskundige Behandelingsovereenkomst (WGBO) or Medical Treatments Contracts Act
- Algemene Verordening Gegevensbescherming (AVG) or General Data Protection Regulation (GDPR)

2. Data Collection

2.1 Give a short description of the research data.

| Subjects | Volume | Data Source | Data Capture Tool | File Type | Format |
|----------|--------|----------------------|-------------------------------|-------------------|--------|
| Human | 500 | EPD | Secured server, Julius Centre | Quantitative data | .csv |
| Human | 50 | Questionnaires | Castor | Quantitative data | .csv |
| Human | 100 | Voice recordings | Secured server, Julius Centre | Qualitative data | m4.a |
| Human | 100 | Transcripts | Secured server, Julius center | Qualitative data | .doc |
| Human | 25 | observations/reports | Secured server, Julius Center | Qualitative data | .doc |

2.2 Describe the flow of the data (name systems used and/or third parties, recipients) <add link to location where diagram is stored in RFS>

Nursing teams and the contact person working at Icare and AxionContinu select eligible patients --> nursing teams ask patients and their family caregiver to fill in the surveys --> surveys are handed out to the research team through the contact person of each nursing team --> research team store the data in Castor and analyse the data with R and/or SPSS.

Alongside the effect study a process evaluation will be carried out. This process evaluation is not mentioned in the study protocol of SMEtH, but has its own individual protocol. The flow of the data for the process evaluation part of this study is as follows: Zorgbelang Inclusief will guide the discussions with the focus groups --> observations are made by the research team during the focus groups --> observations focus groups are reported in Word.

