2.8 Which contracts are in place?

| Organization | Contract Type with UMCU | Role organization |
|-----------------------------------|-------------------------|--|
| AxionContinu | Consortium Agreement | Homecare organization where the intervention will be implemented and patients and family caregivers will be studied. |
| Zorgbelang Inclusief | Consortium Agreement | advisory and participatory role by guiding the conversation with the healthcare professionals as part of the process evaluation and by taking part in the development of end products. |
| Icare | Consortium Agreement | Homecare organization where the intervention will be implemented and patients and family caregivers will be studied. |
| ROC Midden Nederland | Consortium Agreement | advisory and participatory role by participating in guiding panels in to develop end products that are adapted to the education system |
| Hogeschool Utrecht | Consortium Agreement | advisory and participatory role by participating in guiding panels in to develop end products that are adapted to the education system |
| Integraal Kankercentrum Nederland | Consortium Agreement | advisory and participatory role by participating in the steering group and taking part in the development of end products. |
| | | |

2.9 State how ownership of the data and intellectual property rights (IPR) to the data will be managed

Data will be collected by researchers of the EPZU research team. In collecting Data the research team will not be collaborating with other parties.

Contact persons in each nursing team will be in contact with all individual participants. If the decision is made to use local researchers to collect data from participants instead of researchers of the EPZU, in light of the feasibility of the study, a contract will be drafted that fit the tasks and responsibilities of that specific context. Consequently, this DMP will be adjusted according to the latest amendments.

2.10 Use of new technology. Does your study involve the implementation of a technology that has not been used before at UMC Utrecht?

- No

2.12 Will the study need/use personal data (directly or indirectly identifying) from the Electronic Patient Files (EPD; HiX), DNA, body material, images or any other form of personal data?

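### The USD-4D is both the tool of Palliative Reasoning step 1 and an outcome in both arms, and the plan does not keep completed outcome forms away from the nursing teams, so control teams may be exposed to part of step 1

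*Protocol*

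**What the plan says.** **Role in the intervention.** Protocol section 3 describes four PR steps, the first being to map the patient's situation, symptom burden and quality of life. The USD-4D "will be used to monitor the individual situation, symptom burden and quality of life of patients, as described in step 1".

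**Role as an outcome.** Protocol 5.1.2: "Symptom burden of patients is assessed at enrolment, at one, three and six months by means of the Utrecht Symptom Diary Four Dimensional (USD4D"). Protocol 5.2: "patients will complete at one-, three- and six-months a questionnaire containing questions regarding symptom control, quality of life and symptom burden". Neither sentence is limited to one arm, so control patients complete the USD-4D too.

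**Control condition.** Section 3: "The nursing teams selected as control group will continue to provide usual care to patients with a life-limiting illness". It does not say whether control teams may see or use USD-4D answers given for the study.

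**Who handles the forms.** There are four statements:
- Protocol 5.2, procedures: "the research team will perform an assessment of baseline measurements in participating patients".
- Protocol 5.2, Blinding: "the data are collected by local nurses who are aware of their allocation".
- Data Management Plan (the document filed as the SAP), 2.2: nursing teams ask patients and caregivers to complete the surveys, and "surveys are handed out to the research team through the contact person of each nursing team".
- Data Management Plan, 2.9: "Data will be collected by researchers of the EPZU research team".

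**Analysis.** Protocol 6.2 plans joint longitudinal models per symptom and does not mention the dual role.

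**The concern.** Two separate effects are possible.

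1. **Exposure of control teams.** If completed forms pass through a control team, that team can see a four-dimensional symptom map of its own patient, which is the material PR step 1 is meant to produce. The enrolment form is completed one month before the primary answer. Any response by the team would move usual care towards PR and shrink the primary contrast.

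2. **Different use of the scale.** In the intervention arm the USD-4D is a care instrument shared with the nurse in an open-label trial. In the control arm it is only a research form. Later USD-4D scores may then differ between arms through familiarity with the form or its perceived purpose, as well as through symptoms. Of the patient outcomes, it is the only one that the protocol describes as covering the physical, psychological, social and spiritual dimensions, which are PR's stated focus.

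**Working it through.** **Step 1: the handling statements side by side.**

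| Place | Who handles the data | Could a control team see the form? |
|---|---|---|
| Protocol 5.2, procedures | Research team, for baseline; by post, mail, telephone or teleconsultation | Not by this route |
| Protocol 5.2, Blinding | Local nurses who know the allocation | Yes |
| Data Management Plan 2.2 | Nursing team asks; contact person passes on | Yes |
| Data Management Plan 2.9 | Research team; a change to local researchers would need a contract and an amended plan | Not by this route |

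The research-team statement in 5.2 covers baseline. For the patients' follow-up questionnaires, 5.2 gives no route. Following the Blinding text and Data Management Plan 2.2 as written would put completed forms in control teams' hands. No passage asks for sealed forms or tells teams not to read them.

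**Step 2: care forms and outcome forms.** No passage says whether USD-4D sheets completed in care are separate from the outcome forms. Protocol 5.2 also places team training before the patients' baseline, and Data Management Plan 2.4 says quantitative data are gathered after implementation. The enrolment score in the intervention arm may therefore come after the team has begun using the tool.

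**Step 3: reproduce the stated sample size.** Inputs from Protocol 4.4: 30% v 40%, 20 patients per cluster, ICC 0.001, power 80%, alpha 5%. The protocol does not state sidedness; two-sided is assumed here. With k clusters per arm:

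- Design effect = 1 + (20 − 1) × 0.001 = 1.019
- SE = √{[p₁(1 − p₁) + p₀(1 − p₀)] × 1.019 / (20k)}
- Power = P(T ≤ |p₁ − p₀|/SE − t₀.₉₇₅), where T and t₀.₉₇₅ have 2(k − 1) degrees of freedom

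At k = 20: SE = √(0.45 × 1.019 / 400) = 0.0339; 0.10/0.0339 = 2.953; 2.953 − 2.024 = 0.929; power 82.1%. At k = 19, power is 79.97%, just under 80%, so k = 20 as stated. The same method gives 26, 23 and 21 for ICC 0.02, 0.01 and 0.005, matching Table 1. For the 60% rows it gives 4, 4, 4, 4 against the stated 5, 4, 4, 4, which does not affect this point.

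**Step 4: sensitivity to a shift in the control rate.** The documents give no contamination rate. The control rates above 30% are assumptions, with the intervention rate held at 40% and 20 clusters of 20 per arm.

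| Control rate | SE (ICC 0.001) | Difference/SE | Power, ICC 0.001 | Power, ICC 0.02 | Clusters per arm for 80%, ICC 0.001 |
|---|---|---|---|---|---|
| 30% (plan) | 0.0339 | 2.953 | 82% | 69% | 20 |
| 31% | 0.0340 | 2.647 | 73% | 60% | 24 |
| 32% | 0.0341 | 2.343 | 62% | 50% | 30 |
| 33% | 0.0343 | 2.042 | 51% | 39% | 39 |

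**Step 5: scale-use effect.** This cannot be computed. The documents give no standard deviation, target difference or reporting shift for the USD-4D.

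**The case against.** A reader might infer that control patients receive part of PR. The documents do not support that. Step 1 is mapping that feeds a plan, an evaluation and an adjustment by the team. A control patient who fills in a form seen only by researchers is being measured, not treated. Exposure arises only if the team sees the scores, dilution only if it responds to them, and no passage says control nurses do either. Protocol 5.2 (procedures) and Data Management Plan 2.9 point towards collection by researchers.

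A reader might also infer that the USD-4D comparison cannot be interpreted at all. That does not follow either. The frequency of USD-4D use in care is not stated, and the tool is named for step 1 only. Both arms share the outcome schedule, so familiarity is partly common to both. The direction and size of any bias are unknown.

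Three further objections stand. Both arms are already screened for symptoms with the Distress Thermometer problem list and offered specialist nurse support after each questionnaire, so the added exposure from the USD-4D alone cannot be isolated. Usual care has still to be described, so it is unknown whether this kind of mapping is new to control teams. And the power figures show how sensitive the design is to any rise in the control rate; they are not evidence that this mechanism causes one.

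What the objections do not remove is that two passages route forms through the nursing teams, two do not, and no safeguard is written.

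**Conclusion.** The point holds as a risk that the plan leaves open and could close cheaply. The dual role of the USD-4D and its use in both arms are on the page, and the handling passages contradict each other. If the nursing-team route is followed, control teams may be exposed to part of PR step 1 before the primary answer, and the primary contrast could be diluted by an unknown amount. Under an assumed rise of one or two percentage points in the control rate, power falls from about 82% to about 73% or 62%, at the planned ICC of 0.001 and with the intervention rate unchanged. Separately, the USD-4D difference may partly reflect different use of the scale, in an unknown direction. That effect concerns a secondary outcome; the primary yes/no item is touched only through dilution.

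The finding does not require the EORTC QLQ-C15-PAL to become the lead secondary. The protocol sets no order among the secondary outcomes and describes the USD-4D as validated in palliative care. The QLQ-C15-PAL comes from a cancer organisation, while the trial enrols a wide range of diagnoses.

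**What to change.** 1. Reconcile Protocol 5.2 (procedures and Blinding) with Data Management Plan 2.2 and 2.9. State one route for both arms and all time points: outcome questionnaires go directly from patient to research team, by sealed or direct post, telephone or online. Protocol 5.2 already allows remote modes at baseline, so this mainly extends them to follow-up.
2. State that scores from the research forms are not passed to the nursing team in either arm.
3. In Protocol 5.1.2, state that only the research forms supply USD-4D outcome data and that sheets completed in care do not.
4. In Protocol 6.2, state the dual use as a limitation when the USD-4D result is interpreted.

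The cost is wording in two documents, envelopes or direct entry, and slightly more handling by the research team. Some intervention patients may complete the USD-4D twice, once in care and once for research, which works against the protocol's aim of limiting burden. No extra patients or clusters are needed. The change has to be made before collection, because exposure of control teams cannot be undone afterwards.
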